5.3.5.8 Preexisting Medical Conditions

A preexisting medical condition is one that is present at the screening visit for this study. Such conditions should be recorded on the General Medical History and Baseline Conditions eCRF.

A preexisting medical condition should be recorded as an adverse event only if the frequency, severity, or character of the condition worsens during the study. When recording such events on the Adverse Event eCRF, it is important to convey the concept that the preexisting condition has changed by including applicable descriptors (e.g., "more frequent headaches").

5.3.5.9 Worsening of Autism Spectrum Disorder

Medical occurrences or symptoms of deterioration that are anticipated as part of ASD should be recorded as an adverse event if judged by the investigator to have unexpectedly worsened in severity or frequency or changed in nature at any time during the study. When recording an unanticipated worsening of symptoms related to ASD on the Adverse Event eCRF, it is important to convey the concept that the condition has changed by including applicable descriptors (e.g., "accelerated worsening of autism).

5.3.5.10 Hospitalization or Prolonged Hospitalization

Any adverse event that results in hospitalization (i.e., inpatient admission to a hospital) or prolonged hospitalization should be documented and reported as a serious adverse event (per the definition of serious adverse event in Section 5.2.2), except as outlined below.

An event that leads to hospitalization under the following circumstances should not be reported as an adverse event or a serious adverse event:

- Hospitalization for respite care
- Hospitalization for a preexisting condition, provided that all of the following criteria are met:
 - The hospitalization was planned prior to the study or was scheduled during the study when elective surgery became necessary because of the expected normal progression of the disease
 - The subject has not suffered an adverse event
- Prolonged hospitalization due to lack of home care facilities, caregiver issues, transport issues, and so on.

An event that leads to hospitalization under the following circumstances is not considered to be a serious adverse event, but should be reported as an adverse event instead:

- Hospitalization that was necessary because of patient requirement for outpatient care outside of normal outpatient clinic operating hours

5.3.5.11 Cases of Overdose, Medication Error, Drug Abuse, or Drug Misuse

Overdose (accidental or intentional), medication error, drug abuse, and drug misuse (hereafter collectively referred to as "special situations"), are defined as follows:

- Accidental overdose: accidental administration of a drug in a quantity that is higher than the assigned dose
- Intentional overdose: intentional administration of a drug in a quantity that is higher than the assigned dose

- Medication error: accidental deviation in the administration of a drug
In some cases, a medication error may be intercepted prior to administration of the drug.
- Drug abuse: intentional excessive use of a drug that may lead to addiction or dependence, physical harm, and/or psychological harm
- Drug misuse: intentional deviation in the administration of a drug that does not qualify as drug abuse
In cases where drug is to be self-administered by the subject, drug misuse could involve the drug being administered to someone other than the subject.

Special situations are not in themselves adverse events, but may result in adverse events. Each adverse event associated with a special situation should be recorded separately on the Adverse Event eCRF. If the associated adverse event fulfills seriousness criteria, the event should be reported to the Sponsor immediately (i.e., no more than 24 hours after learning of the event; see Section 5.4.2). For balovaptan, adverse events associated with special situations should be recorded as described below for each situation:

- Accidental overdose: Enter the adverse event term. Check the "Accidental overdose" and "Medication error" boxes.
- Intentional overdose: Enter the adverse event term. Check the "Intentional overdose" box. If drug abuse is suspected, check the "Drug abuse" box. If drug abuse is not suspected, check the "Drug misuse" box.
- Medication error that does not qualify as an overdose: Enter the adverse event term. Check the "Medication error" box.
- Medication error that qualifies as an overdose: Enter the adverse event term. Check the "Accidental overdose" and "Medication error" boxes.
- Drug abuse that does not qualify as an overdose: Enter the adverse event term. Check the "Drug abuse" box.
- Drug abuse that qualifies as an overdose: Enter the adverse event term. Check the "Intentional overdose" and "Drug abuse" boxes.
- Drug misuse that does not qualify as an overdose: Enter the adverse event term. Check the "Drug misuse" box.
- Drug misuse that qualifies as an overdose: Enter the adverse event term. Check the "Intentional overdose" and "Drug misuse" boxes.

In addition, all special situations associated with balovaptan, regardless of whether they result in an adverse event, should be recorded on the Adverse Event eCRF as described below:

- Accidental overdose: Enter the drug name and "accidental overdose" as the event term. Check the "Accidental overdose" and "Medication error" boxes.

- Intentional overdose: Enter the drug name and "intentional overdose" as the event term. Check the "Intentional overdose" box. If drug abuse is suspected, check the "Drug abuse" box. If drug abuse is not suspected, check the "Drug misuse" box.
- Medication error that does not qualify as an overdose: Enter the name of the drug administered and a description of the error (e.g., wrong dose administered, wrong dosing schedule, incorrect route of administration, wrong drug, expired drug administered) as the event term. Check the "Medication error" box.
- Medication error that qualifies as an overdose: Enter the drug name and "accidental overdose" as the event term. Check the "Accidental overdose" and "Medication error" boxes. Enter a description of the error in the additional case details.
- Intercepted medication error: Enter the drug name and "intercepted medication error" as the event term. Check the "Medication error" box. Enter a description of the error in the additional case details.
- Drug abuse that does not qualify as an overdose: Enter the drug name and "drug abuse" as the event term. Check the "Drug abuse" box.
- Drug abuse that qualifies as an overdose: Enter the drug name and "intentional overdose" as the event term. Check the "Intentional overdose" and "Drug abuse" boxes.
- Drug misuse that does not qualify as an overdose: Enter the drug name and "drug misuse" as the event term. Check the "Drug misuse" box.
- Drug misuse that qualifies as an overdose: Enter the drug name and "intentional overdose" as the event term. Check the "Intentional overdose" and "Drug misuse" boxes.
- Drug administered to someone other than the subject: Enter the drug name and "subject supplied drug to third party" as the event term. Check the "Drug misuse" box.

As an example, an accidental overdose that resulted in a headache would require two entries on the Adverse Event eCRF, one entry to report the accidental overdose and one entry to report the headache. The "Accidental overdose" and "Medication error" boxes would need to be checked for both entries.

5.3.5.12 Observer-Reported Outcome Data

Adverse event reports will not be derived from ObsRO data by the Sponsor, and safety analyses will not be performed using ObsRO data. Sites are not expected to review the ObsRO data for adverse events.

5.4 IMMEDIATE REPORTING REQUIREMENTS FROM INVESTIGATOR TO SPONSOR

Certain events require immediate reporting to allow the Sponsor to take appropriate measures to address potential new risks in a clinical trial. The investigator must report such events to the Sponsor immediately; under no circumstances should reporting take place more than 24 hours after the investigator learns of the event. The following is a list

of events that the investigator must report to the Sponsor within 24 hours after learning of the event, regardless of relationship to study drug:

- Serious adverse events (defined in Section 5.2.2; see Section 5.4.2 for details on reporting requirements)
- Adverse events of special interest (defined in Section 5.2.3; see Section 5.4.2 for details on reporting requirements)

For serious adverse events and adverse events of special interest, the investigator must report new significant follow-up information for these events to the Sponsor immediately (i.e., no more than 24 hours after becoming aware of the information). New significant information includes the following:

- New signs or symptoms or a change in the diagnosis
- Significant new diagnostic test results
- Change in causality based on new information
- Change in the event's outcome, including recovery
- Additional narrative information on the clinical course of the event

Investigators must also comply with local requirements for reporting serious adverse events to the local health authority and Institutional Review Board/Ethics Committee (IRB/EC).

5.4.2 Reporting Requirements for Serious Adverse Events and Adverse Events of Special Interest

5.4.2.1 Events That Occur prior to Study Drug Initiation

After informed consent has been obtained but prior to initiation of study drug, only serious adverse events caused by a protocol-mandated intervention should be reported. The paper Clinical Trial Serious Adverse Event/Adverse Event of Special Interest Reporting Form provided to investigators should be completed and submitted to the Sponsor or its designee immediately (i.e., no more than 24 hours after learning of the event), either by faxing or by scanning and emailing the form using the fax number or email address provided to investigators.

5.4.2.2 Events That Occur after Study Drug Initiation

After initiation of study drug, serious adverse events and adverse events of special interest will be reported until 2 weeks after the final dose of study drug. Investigators should record all case details that can be gathered immediately (i.e., within 24 hours after learning of the event) on the Adverse Event eCRF and submit the report via the electronic data capture (EDC) system. A report will be generated and sent to Roche Safety Risk Management by the EDC system.

In the event that the EDC system is unavailable, the paper Clinical Trial Serious Adverse Event/Adverse Event of Special Interest Reporting Form provided to investigators should be completed and submitted to the Sponsor or its designee immediately (i.e., no more than 24 hours after learning of the event), either by faxing or by scanning and emailing the form using the fax number or email address provided to investigators. Once the EDC system is available, all information will need to be entered and submitted via the EDC system.

Instructions for reporting serious adverse events that occur > 2 weeks after the final dose of study treatment are provided in Section 5.6.

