5.3.1 Adverse Event Reporting Period

Investigators will seek information on adverse events at each subject contact. All adverse events, whether reported by the subject or noted by study personnel, will be recorded in the subject’s medical record and on the Adverse Event eCRF.

After informed consent has been obtained but prior to initiation of study drug, only serious adverse events caused by a protocol-mandated intervention (e.g., invasive procedures such as biopsies, discontinuation of medications) should be reported (see Section 5.4.2 for instructions for reporting serious adverse events).

After initiation of study drug, all adverse events will be reported until 6 weeks after the final dose of study drug.

Instructions for reporting adverse events that occur after the adverse event reporting period are provided in Section 5.6.

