5.6 ADVERSE EVENTS THAT OCCUR AFTER THE ADVERSE EVENT REPORTING PERIOD

The Sponsor should be notified if the investigator becomes aware of any serious adverse event that occurs after the end of the adverse event reporting period (defined as 6 weeks after the final dose of study drug), if the event is believed to be related to prior study drug treatment. These events should be reported through use of the Adverse Event eCRF. However, if the EDC system is not available, the investigator should report these events directly to the Sponsor or its designee, either by faxing or by scanning and emailing the paper Clinical Trial Serious Adverse Event/Adverse Event of Special Interest Reporting Form using the fax number or email address provided to investigators.

5.7 EXPEDITED REPORTING TO HEALTH AUTHORITIES, INVESTIGATORS, INSTITUTIONAL REVIEW BOARDS, AND ETHICS COMMITTEES

The Sponsor will promptly evaluate all serious adverse events and adverse events of special interest against cumulative product experience to identify and expeditiously communicate possible new safety findings to Investigators, IRBs, ECs, and applicable health authorities based on applicable legislation.

To determine reporting requirements for single adverse event cases, the Sponsor will assess the expectedness of these events using the following reference document as "Reference Safety Information":

- Balovaptan Investigator's Brochure

[REDACTED]

The Sponsor will compare the severity of each event and the cumulative event frequency reported for the study with the severity and frequency reported in the applicable reference document.

Reporting requirements will also be based on the investigator's assessment of causality and seriousness, with allowance for upgrading by the Sponsor as needed.

The IMC and the independent SOC will monitor the incidence of these expected events during the study. An aggregate report of any clinically relevant imbalances that do not favor the test product will be submitted to health authorities.

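### Section 5.4.2.2 ends SAE and AESI reporting at 2 weeks after the last dose, against 6 weeks in 5.3.1 and 5.6, and its onward reference to 5.6 does not cover the interval between

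*Combined protocol and SAP*

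**What the plan says.** Four sections of the protocol bear on this.

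- **5.3.1 (Adverse Event Reporting Period):** once study drug has started, "all adverse events will be reported until 6 weeks after the final dose of study drug".
- **5.4 (Immediate Reporting Requirements):** SAEs and AESIs are events that the investigator "must report to the Sponsor within 24 hours after learning of the event, regardless of relationship to study drug". No end date is given, and the section refers to 5.4.2 for the details.
- **5.4.2.2 (Events That Occur after Study Drug Initiation):** "serious adverse events and adverse events of special interest will be reported until 2 weeks after the final dose of study drug". It adds: "Instructions for reporting serious adverse events that occur > 2 weeks after the final dose of study treatment are provided in Section 5.6".
- **5.6 (late events):** this section asks sites to tell the sponsor about SAEs, and names no other kind of event. It fixes when it starts and adds a causality condition in these words: "reporting period (defined as 6 weeks after the final dose of study drug), if the event is believed to be related to prior study drug". On the route, it says: "These events should be reported through use of the Adverse Event eCRF".

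**The concern.** Section 5.2.2 defines an SAE as a kind of adverse event, so 5.3.1 makes it reportable for 6 weeks while 5.4.2.2 stops at 2. Read literally, the most serious events have the shorter window. The onward reference does not repair this, because it leads to a section that has not yet come into effect and that carries a narrower rule.

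What is at stake is whether two rules still hold between weeks 2 and 6: report within 24 hours, and report regardless of relationship. A site that relies on 5.3.1 and 5.4 would apply both. A site that goes from 5.4.2.2 to 5.6 could drop the 24-hour limit or wrongly screen out events it judges unrelated. Under 5.7 the sponsor may upgrade the investigator's assessment of causality and seriousness, but it cannot upgrade an event it never receives.

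**Working it through.** There is no stated figure to reproduce. The check compares the sections and takes one difference.

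**Windows.** 5.3.1 and 5.6: 6 weeks = 42 days. 5.4.2.2: 2 weeks = 14 days. Interval in conflict: 42 − 14 = 28 days (days 15 to 42 after the final dose), which is 28/42 = 67% of the post-dose reporting period in 5.3.1.

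**What each section requires for an SAE, by days after the final dose**

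| Section | Days 1–14 | Days 15–42 | After day 42 |
|---|---|---|---|
| 5.3.1 | Report | Report | Period over; refers to 5.6 |
| 5.4 | 24 hours, any causality | 24 hours, any causality (no end date) | No end date stated |
| 5.4.2.2 | Report within 24 hours | Window closed; refers to 5.6 | Refers to 5.6 |
| 5.6 | Not yet in effect | Not yet in effect | Related SAEs only; no time limit stated |

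The middle column holds the conflict. The submission route is not in dispute: 5.4.2.2 and 5.6 both use the Adverse Event eCRF, with the paper form if the EDC system is down.

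**References into 5.4.2.** Seven sections send the site there for events after the start of study drug: 5.2.2, 5.2.3, 5.3.5.3, 5.3.5.6, 5.3.5.7, 5.3.5.11 and 5.4. From day 15 all seven lead to a closed window.

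**Two worked cases**

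1. *Death on day 30.* Section 5.3.5.7 requires immediate reporting whatever the causality, because day 30 lies inside the 5.3.1 period, and refers to 5.4.2. There the window closed after day 14. The next reference is to 5.6, which begins after day 42 and asks only for related SAEs. The duty is clear in 5.3.5.7; the instructions it relies on are not.
2. *Non-serious AESI on day 20.* Section 5.4.2.2 has ended, and its onward reference names SAEs only. The notification rule in 5.6 also names only SAEs. The AESI has no onward instruction from 5.4.2.2, although 5.4 still lists it as immediately reportable.

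**The case against.** The strongest reply is that the duty survives. Section 5.4 sets the 24-hour, any-causality rule without an end date and in emphatic terms; 5.2.2 and 5.2.3 repeat the 24-hour duty. Section 5.6 limits itself to events after 6 weeks, so its related-only condition does not apply on day 30. Section 5.3.5.7 also says that deaths go to 5.6 only once the reporting period is over. On this view, harm requires a site to misread 5.6 and overlook 5.3.1 and 5.4.

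That is right as far as it goes, and it rules out any claim that these events go wholly unreported. It does not remove the contradiction. The sections that carry the duty rely on 5.4.2 for its execution, 5.4.2.2 itself directs the site to 5.6, and nothing in the visible text says which section prevails.

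Three narrower points stand:

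- The related-only condition, if misapplied, would remove only SAEs judged unrelated. SAEs judged related would still be notified, possibly late.
- The 67% describes the width of the overlap, not harm. Over a subject's whole span from first dose, the 4 weeks are 4/(6 + 6) = 33% without the extension, or 4/(54 + 6) = about 7% with it.
- The last visit in the visible text is 2 weeks after the final dose, so later events depend largely on sites learning of them outside visits. The schedules of activities are redacted, and other contacts cannot be checked.

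**Conclusion.** The contradiction holds and must be fixed. A mandatory safety-reporting duty has two incompatible end dates, and the reference meant to bridge them does not cover the 28 days between. The conclusion rests on current, unredacted text and on no assumption about event rates; the documents give no expected SAE rate for this interval, so the number of affected reports cannot be estimated.

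The severity rests on one consequence: a delayed or wrongly withheld SAE report, or an AESI left without clear instructions, in very young children. Nothing in the primary PK analysis changes, and treatment-period incidence is unaffected because Section 6.5 summarizes follow-up data separately. The documents do not show whether 2 or 6 weeks was intended.

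**What to change.** Reconcile 5.3.1, 5.4.2.2 and 5.6 to one end date for AEs, SAEs and AESIs. The choice is the sponsor's; a single date fits the single reporting period that 5.3.5.7 and 5.6 already assume. Reword the last sentence of 5.4.2.2 so that the reference to 5.6 takes effect when that period ends. The seven references to 5.4.2 then work unchanged.

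If the chosen period runs beyond the 2-week follow-up visit, the sponsor should check that the remaining time is covered by some contact with the family.

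The cost is wording in up to three sections. Sample size and analyses do not change.

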5.5 FOLLOW-UP OF SUBJECTS AFTER ADVERSE EVENTS

5.5.1 Investigator Follow-Up

The investigator should follow each adverse event until the event has resolved to baseline grade or better, the event is assessed as stable by the investigator, the subject is lost to follow-up, or the subject's parent or legal guardian withdraws consent. Every effort should be made to follow all serious adverse events considered to be related to study drug or trial-related procedures until a final outcome can be reported.

During the study period, resolution of adverse events (with dates) should be documented on the Adverse Event eCRF and in the subject's medical record to facilitate source data verification. If, after follow-up, return to baseline status or stabilization cannot be established, an explanation should be recorded on the Adverse Event eCRF.

5.5.2 Sponsor Follow-Up

For serious adverse events and adverse events of special interest, the Sponsor or a designee may follow up by telephone, fax, email, and/or a monitoring visit to obtain additional case details and outcome information (e.g., from hospital discharge summaries, consultant reports, autopsy reports) in order to perform an independent medical assessment of the reported case.

5.6 ADVERSE EVENTS THAT OCCUR AFTER THE ADVERSE EVENT REPORTING PERIOD

The Sponsor should be notified if the investigator becomes aware of any serious adverse event that occurs after the end of the adverse event reporting period (defined as 6 weeks after the final dose of study drug), if the event is believed to be related to prior study drug treatment. These events should be reported through use of the Adverse Event eCRF. However, if the EDC system is not available, the investigator should report these events directly to the Sponsor or its designee, either by faxing or by scanning and emailing the paper Clinical Trial Serious Adverse Event/Adverse Event of Special Interest Reporting Form using the fax number or email address provided to investigators.

5.7 EXPEDITED REPORTING TO HEALTH AUTHORITIES, INVESTIGATORS, INSTITUTIONAL REVIEW BOARDS, AND ETHICS COMMITTEES

The Sponsor will promptly evaluate all serious adverse events and adverse events of special interest against cumulative product experience to identify and expeditiously communicate possible new safety findings to Investigators, IRBs, ECs, and applicable health authorities based on applicable legislation.

To determine reporting requirements for single adverse event cases, the Sponsor will assess the expectedness of these events using the following reference document as "Reference Safety Information":

- Balovaptan Investigator's Brochure

[REDACTED]

The Sponsor will compare the severity of each event and the cumulative event frequency reported for the study with the severity and frequency reported in the applicable reference document.

Reporting requirements will also be based on the investigator's assessment of causality and seriousness, with allowance for upgrading by the Sponsor as needed.

The IMC and the independent SOC will monitor the incidence of these expected events during the study. An aggregate report of any clinically relevant imbalances that do not favor the test product will be submitted to health authorities.

